### 3. Introduction

#### 3.1. Background

Early postsurgical period is associated with high incidence of postoperative pulmonary complications, including pneumonia, aspiration pneumonitis, respiratory failure, re-intubation within 48h, weaning failure, pleural effusion, atelectasis, bronchospasm, and pneumothorax. The reported incidence rates range from 2 to 40% depending on context. Estimates suggest that more than 1 million postoperative pulmonary complications occur annually in the United States, with 46, 200 related deaths and 4.8 million additional hospitalization days. ISOS and EUSOS studies showed that in Europe the incidence of postsurgical critical events and in-hospital mortality are also significant.

Patients with one or more pulmonary complications, even mild, have up to 48% increased early postoperative mortality and up to 91% increased intensive care unit (ICU) admission. In the case of postoperative pulmonary complications, a mean increase of hospital length of stay of approximately 8 days and a cost of surgery from 2 to 12-fold higher were also reported.

The most frequent severe postoperative respiratory complication is respiratory failure, defined as unexpected tracheal re-intubation, need for postoperative mechanical ventilation, postoperative acute lung injury and acute respiratory distress syndrome, with a reported incidence ranging between 0.2 and 3.4%. Main predictive risk factors for hypoventilatory respiratory failure are obesity, breathing disorder conditions (e.g., obstructive sleep apnea), and postsurgical use of anesthetic and analgesic medications. Respiratory failure is reported to contribute to increased hospital stay, cost of care and 30-days readmission rate.

Different scores have been developed to try predicting postoperative respiratory complications and mortality. Main reported predictors include (but are not limited to) older age, preoperative low SpO2, previous respiratory infections, preoperative anemia, intrathoracic/upper abdominal surgical incision, concomitant cardiac disease, diabetes, surgery duration and emergency procedure.

Postoperative hypoxemia it is a strong indicator of patient instability, compromises wound healing and promotes other serious complications, including brain dysfunction, dysrhythmias and myocardial ischemia. Prolonged hypoxic episodes have been reported to be common in hospitalized patients recovering from non-cardiac surgery: up to 37% of patients had at least one episode of oxygen saturation < 90% lasting more than one hour while 3% had saturations <80% for at least 30 minutes.

Postsurgical patients at-risk of developing cardiopulmonary complications could benefit from both preventive interventions and more intensive postsurgical monitoring. Up to 84% of in-hospital cardiopulmonary arrest events are preceded by prolonged periods of physiological and clinical instability. Early intervention of clinically unstable patients by a medical emergency team significantly reduces the incidence of, and mortality from, unexpected cardiac arrest in hospital. A significant decrease in the number of cases of respiratory failure, stroke, severe sepsis, and acute renal failure was also shown after the implementation of a medical emergency team in an Australian study. In 2007, the UK National Institute for Health and Clinical Excellence recommended the use of physiological track and trigger systems to monitor adult patients in acute hospital settings: these systems, also known as Early Warning Scores (EWS), are based on the monitoring of patients' basic physiological observations such as pulse rate, SpO2, blood pressure, respiration rate, temperature and conscious level and are used to identify patients at risk of respiratory failure, cardiac arrest and death. A systematic review has reported that EWS have a strong predictive value for the occurrence of cardiac arrest and death within 48 hours of measurement. EWS has been demonstrated to be effective in predicting clinical deterioration that may lead to a cardiac arrest also in patients in wards that are poorly equipped to detect rapid patient deterioration. National EWS (NEWS), based upon common vital signs such as temperature, respiratory rate, heart rate, systolic blood pressure, nursing assessments of consciousness level of the patient, SpO2 and use of supplemental oxygen is one of the most frequently utilized.

Respiratory compromise (RC) is a state in which there is a high likelihood of decompensation into respiratory depression, respiratory failure or death, but in which specific interventions (enhanced monitoring and/or therapies) might prevent or mitigate decompensation. Patients with RC have up to a two-fold increase in mortality following delayed medical emergency team activation. Detecting a patient's declining RC status before progression to respiratory depression in patients continuously monitored in the general ward could allow earlier intervention, thus potentially decreasing adverse outcomes.

Due to possibly improved patient safety, continuous SpO2 and capnography monitoring combined with automated decision support tools to determine potential or established patient critical illness are starting to have an important role also outside ICU. Current standard of care for respiratory monitoring of high risk hospital ward patients, such as those receiving opioid therapy, is intermittent documentation of SpO2 value (e.g. spot checks performed at 4 to 6 hours intervals). Respiratory rate (RR) is often determined by clinician assessment though manual inaccurate respiration counts.

Growing evidence supports the use of capnography for earlier and more reliable warnings of potential RC in postoperative patients in the general ward, compared with pulse oximetry. Capnography monitoring has also been associated with in-hospital mortality in emergency department patients with cardiac arrest and suspected sepsis across a range of disease severity.

There are no data on the real incidence and severity of potential RC markers and their correlation with cardiopulmonary or other complications in European postsurgical patients. A pilot study on this topic could be useful to collect information on the utility of continuous SpO2 and capnography monitoring in this setting and to develop future clinical evidence. This study may also provide the data needed to evaluate certain health-economic outcomes associated with introduction of continuous monitoring in the general ward setting.

## 3.2. Purpose

The main purpose of this study is to quantify the incidence and the severity of postoperative RC markers on high risk postsurgical patients on a general ward.

## 4. Objectives and Endpoints

### 4.1. Objectives

#### 4.1.1. Primary Objective and Endpoint

The primary objective of this study is to quantify the incidence of RC markers in high risk postsurgical patients, using a system comprised of two continuous monitoring devices, connected to a remote monitoring platform.

The occurrence of at least one of the following RC markers will be considered as primary endpoint for patients monitored by Capnostream 20p during both study Phases:

1. SpO2 ≤ 90% for ≥ 3 minutes.
2. RR ≤ 8 or ≥ 22 bpm for ≥ 3 minutes.
3. etCO2 ≤ 15 or ≥ 60 mmHg for ≥ 3 minutes.
4. Apnea episode lasting > 30 seconds.

The occurrence of at least one of the following RC markers will be considered as primary endpoint for patients monitored by PM1000N-RR during both study Phases:

1. SpO2 ≤ 90% for ≥ 3 minutes.
2. RR ≤ 8 or ≥ 22 bpm for ≥ 3 minutes.

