Study Design	
LIFEGUARD is a prospective, two-center, two-phase pilot study. The study population consists of post-surgical patients of adult age on the hospital ward at high risk of developing respiratory and cardiovascular events.
 
During the study Phase I, 70 patients will be 1:1 randomly allocated to Capnostream 20p monitoring system or to PM1000N-RR pulse oximeter monitoring system. In this first phase the alarms of both devices will be silenced and the screen information blinded, to establish a baseline for the incidence of respiratory events in continuously monitored high risk patients. After Phase I and before starting Phase II, each participating site will have a minimum of a 1-month period for familiarization with the unblinded devices, based on a pre-defined hospital protocol for alarm management and escalation policy.
 
During the study Phase II, an additional 140 patients will be 1:1 randomly allocated to Capnostream 20p or to PM1000N-RR monitoring but the screen information will be visible at the bedside and through the Vital Sync™ remote patient monitoring system. The nursing staff will respond to device alarms based on a pre-defined alarm management policy.

Sample Size	Approximately 210 patients will be enrolled in 2 European centers. Each participating center may involve one or more wards in the study, based on its distribution of high-risk patients that may benefit from monitoring.
Inclusion/Exclusion Criteria	
The following criteria must be met for inclusion in the study:
 

1. Non-cardiac post-surgical patients at high risk of developing respiratory and cardiovascular events based on both ARISCAT and POSPOM scores on the hospital ward. In particular, to be enrolled a patient must have: POSPOM score <math>\geq 24</math> (<math>> 3</math> times the mortality average risk) OR ARISCAT score <math>\geq 26</math> (High or intermediate risk for postoperative pulmonary complications).

2. Adult age (<math>\geq 18</math> year old).

3. Patient is able and willing to give informed consent.

 
Exclusion criteria (any of the list below):

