### 6.3. End-tidal Carbon Dioxide (etCO2) Sampling Line

A sample of the exhaled gases are delivered from the patient (via a cannula) into the monitor for etCO2 measurement. The etCO2 sample line (also referred to as a filter line) is a disposable single use sampling line. Each study patient will be connected to the Capnostream monitor with an etCO2 sampling line.

Supplemental oxygen may also be delivered through the sampling line, as needed. Any supplemental oxygen, up to 5 lit/min, will be delivered per usual clinical practice. The supplemental oxygen is not provided through the monitor.

Figure 4. etCO2 Sampling Line

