## 8.5 Enrollment

The point of enrollment is completion of informed consent and confirmation of inclusion/exclusion criteria per the screening evaluation.

Data collected for enrolled patients includes:

- Medical history (including surgical, apnea, and medical therapy such as oxygen use and opioid use)
- Demographic & Physical exam
- Vital signs
- Supplemental oxygen use
- Surgery information

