**Appendix E: ARISCAT, POSPOM and NEWS scores calculation****ARISCAT risk score calculation**

High or intermediate risk for postoperative pulmonary complications following abdominal surgery:  
ARISCAT risk score  $\geq 26$

Risk for PPC of Variables Selected for the Logistic Regression Model			
	Multivariate Analysis	<math>\beta</math> Coefficients	Risk Score<math>\ddagger</math>
OR (95% CI) N = 1624			
Age (yr)			
$\leq 50$	1		
$51 - 80$	1.4 (0.6 - 3.3)	0.331	3
$> 80$	5.1 (1.9 - 13.3)	1.619	16
Preoperative SpO2, %			
$\geq 96$	1		
$91 - 95$	2.2 (1.2 - 4.2)	0.802	8
$\leq 90$	10.7 (4.1 - 28.1)	2.375	24
Respiratory infection in the last month			
Preoperative anemia (<math>\leq 10</math> g/dL)	5.5 (2.6 - 11.5)	1.698	17
Surgical incision			
Peripheral	1		
Upper abdominal	4.4 (2.3 - 8.5)	1.480	15
Intrathoracic	11.4 (4.9 - 26.0)	2.431	24
Duration of surgery, h			
$\leq 2$	1		
$> 2$ to $3$	4.9 (2.4 - 10.1)	1.593	16
$> 3$	9.7 (4.7 - 19.9)	2.268	23
Emergency procedure	2.2 (1.04 - 4.5)	0.768	8
Abbreviations: CI, confidence interval; OR, odds ratio; SpO 2 , oxyhemoglobin saturation by pulse oximetry breathing air in supine Position: PPC, postoperative pulmonary complications.			

$\ddagger$  The simplified risk score is the sum of each logistic regression coefficient multiplied by 10, after rounding off its value.

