## 7.9. Evaluation of Objectives

### 7.9.1. Primary Endpoint

The Primary Endpoint of the Study is to quantify the incidence of RC markers in high risk postsurgical patients, using a system comprised of two continuous monitoring devices, connected to a remote monitoring platform. The proportion and rate of “At least one RC marker” event will be calculated and reported.

The “At least one RC marker” event is defined as the occurrence of at least one of the following RC markers:

1.  $\text{SpO}_2 \leq 90\%$  for  $\geq 3$  minutes (or  $\text{SpO}_2 \leq 90\%$  for  $< 3$  min with an action taken);
2.  $\text{RR} \leq 8$  or  $\geq 22$  bpm for  $\geq 3$  minutes (or  $\text{RR} \leq 8$  or  $\geq 22$  bpm for  $< 3$  min with an action taken);
3.  $\text{EtCO}_2 \leq 15$  or  $\geq 60$  mmHg for  $\geq 3$  minutes (or  $\text{EtCO}_2 \leq 15$  or  $\geq 60$  mmHg for  $< 3$  min with an action taken);
4. Apnea episode lasting  $> 30$  seconds.

For patients monitored by PM1000N, only RC markers #1 and #2 will be considered.

RC determination will be assessed by a physician belonging to the “other” site (cross assessment by the sites). This assessment will be made by the analysis of both device and clinical data for each patient. For each patient all potential RC episodes will be derived using the Detection Tool (see Section 10.1) and will be submitted to the other site’s physician in order to adjudicate the potential RC episodes starting from episodes most likely to be RC. The adjudication will stop at the first RC occurring per patient.

The Events’ rates will be computed as (total number of “At least one RC marker” event)/(total number of time-person in PPS) and will be reported separately for each arm and phase of the study. Events’ rates will be displayed together with their 95% confidence interval (95%CI).

If the number of episode per patient result unbalanced, adjusted rates will be reported using the GEE model, together with their 95% confidence interval (95%CI).

If appropriate, also the events’ rates for each RC marker will be reported separately, for each arm and phase of the study.

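### The SpO2 marker shares its absolute cut-off with the top ARISCAT SpO2 item and no analysis uses baseline SpO2, so pre-existing low SpO2 can be counted as postoperative respiratory compromise and can shift the phase comparison

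*Protocol*

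**What the plan says.** Protocol 3.2 states that the study is to "quantify the incidence and the severity of postoperative RC markers on high risk postsurgical patients on a general ward". Protocol 4.1.1 lists "SpO 2 ≤ 90% for ≥ 3 minutes" as the first marker for both devices, and any one marker makes the patient positive. SAP 7.9.1 defines the event as the "occurrence of at least one of the following RC markers", keeps the 90% limit, and also admits shorter episodes that led to an action. The Detection Tool in SAP 10.1 works from the endpoint thresholds. A physician from the other site then adjudicates potential episodes, using device and clinical data.

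Entry (Protocol 7.3) requires POSPOM of at least 24 or ARISCAT of at least 26. In Appendix E, a preoperative SpO2 of 90% or less scores 24 ARISCAT points. The footnote defines this reading as "oxyhemoglobin saturation by pulse oximetry breathing air in supine" position. Protocol 7.4 excludes ventilated or intubated patients but sets no limit on baseline SpO2.

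For secondary endpoint #1, SAP 7.9.2 compares the phases by chi-square or Fisher exact test and adds a Poisson rate ratio if exposure differs. SAP 7.2 mentions a propensity score only as a possibility and names no covariates.

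**The concern.** The headline result will be read as the frequency of respiratory compromise arising after surgery. A patient whose SpO2 was 90% or less before the operation and is unchanged afterwards can meet the marker without any postoperative decline. The low value also raises the score that qualified the patient. The reported proportion can thus combine new events with a pre-existing state, and the planned tables give no way to separate them.

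The phase comparison is exposed for a different reason. Patients are randomised to device within each phase, which balances baseline SpO2 between devices on average. The phases themselves are sequential, at least a month apart, and the planned test is unadjusted. A different share of patients with low baseline SpO2 would appear as a difference between blinded and open monitoring.

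**Working it through.** **1. The plan's own figures.** SAP 6 plans on a proportion of 10%, a 95% interval with 5% precision, and probability of at least 0.80 of reaching it. Taking precision as the half-width of a Clopper-Pearson interval, the smallest n with exact binomial probability of at least 0.80 is 179; at the stated 182 the probability is 0.855. Inflating for losses, 182 × 1.15 = 209.3, or about 210. The SAP figures reproduce, so 10% and 5 points serve as yardsticks below. (Protocol 12.1 gives 260 where the SAP gives 182. That is a separate discrepancy and does not enter here.)

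**2. The route into the study** (points from Appendix E):

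- SpO2 ≤ 90% alone: 24, below 26.
- With age 51–80: 24 + 3 = 27.
- With age over 80: 24 + 16 = 40.
- With an emergency procedure: 24 + 8 = 32.

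The SpO2 item does not admit by itself, but any patient over 50 who has it qualifies.

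**3. Upper bound on the primary proportion.** Let f be the share of analysed patients with preoperative SpO2 ≤ 90%. The documents do not give it; the range 1% to 10% is an assumption. Let p0 be the proportion positive among the rest. If every patient in the share f scores positive:

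observed = f + (1 − f) × p0, and excess over p0 = f × (1 − p0).

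| f (assumed) | observed, p0 = 10% | excess, points | observed, p0 = 37% | excess, points |
|---|---|---|---|---|
| 1% | 10.9% | 0.9 | 37.6% | 0.6 |
| 2% | 11.8% | 1.8 | 38.3% | 1.3 |
| 5% | 14.5% | 4.5 | 40.2% | 3.2 |
| 10% | 19.0% | 9.0 | 43.3% | 6.3 |

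The second anchor is the figure cited in Protocol 3.1: up to 37% of patients with saturation below 90% for more than an hour. At p0 = 10%, the excess equals the planned 5-point precision when f = 0.05 / 0.90 = 5.6%, or about 12 of 210 patients.

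**4. Phase comparison.** Under the same worst case, and with no true difference between phases, the observed difference is (f in Phase II − f in Phase I) × (1 − p0). At p0 = 10%, each percentage point of imbalance in f moves it by 0.9 points. For example, f = 5% in Phase I and 10% in Phase II gives 14.5% against 19.0%, a 4.5-point difference produced by case mix alone. If f is equal in both phases, a real difference is multiplied by (1 − f), that is 0.99 to 0.90 over the assumed range, which is a minor dilution.

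**5. Cell sizes.** Phase I has 35 patients per arm and Phase II has 70. For f of 1% to 10%, the lowest band would hold 0.35 to 3.5 patients per arm in Phase I and 0.7 to 7 in Phase II.

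**The case against.** An absolute threshold is a legitimate choice. The glossary describes RC as a state, not a decline. The same limits appear as the recommended Phase II alarm settings in Appendix B, so the endpoint measures what the monitors would flag. A patient at 90% before surgery who desaturates further is a genuine case, and an estimate that leaves such patients out loses some of those at highest risk. This stands, and it is why the threshold proportion should remain primary.

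The preoperative and ward readings are also taken under different conditions. The ARISCAT value is on air, while on the ward "Any supplemental oxygen, up to 5 lit/min, will be delivered per usual clinical practice". A patient at or below 90% on air may stay above it on oxygen. The adjudicator sees clinical data and can reject an episode. Both points stand and make the figures above upper bounds. They do not close the gap, because no written criterion tells the adjudicator how to treat pre-existing low SpO2.

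Finally, SAP 7.6 compares baseline characteristics and tabulates vital signs, SAP 7.1.3 allows an additional analysis set, and a propensity score is possible. These may reveal an imbalance between phases, but none commits the analysis to correcting for it.

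**Conclusion.** The point holds as a gap in reporting and in confounder control. Patients with pre-existing low SpO2 can be counted as postoperative RC, and the unadjusted comparison for secondary endpoint #1 can shift with the baseline SpO2 mix. The upper bound on the excess is 0.9 to 9.0 points on a true 10%, for an assumed f of 1% to 10%. It rests on every such patient scoring positive. Supplemental oxygen, adjudication, and patients who would be positive anyway through another marker all reduce it. The comparison between devices within a phase is protected on average by randomisation.

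Four stronger readings might be inferred, and the documents support none of them:

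- That the SpO2 item admits patients by itself: 24 is below 26.
- That all such patients will be counted: they must still meet the marker on the ward and pass adjudication.
- That an expected inflation can be calculated, including for the 91–95% band: the documents give neither the case mix nor the within-patient variability of SpO2.
- That apnea or respiratory rate markers can likewise be labelled as present at baseline: Protocol 8.5 records apnea as a history item, and a spot respiratory rate cannot show a 3-minute run.

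**What to change.** Keep the threshold proportion as the primary result.

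- **SAP 7.9.1:** tabulate the primary proportion by arm, phase and baseline SpO2 band (≥ 96, 91–95, ≤ 90), using the ARISCAT bands. Add a sensitivity estimate that excludes patients at ≤ 90% at baseline.
- **SAP 7.9.2:** stratify or adjust the phase comparison for secondary endpoint #1 by that band, for example with a Mantel-Haenszel estimate, or with baseline SpO2 as a covariate where the Poisson model is used.
- **Source of the baseline value:** use the preoperative SpO2 that entered ARISCAT or, where it is not on file, the enrolment vital signs. State which was used. Supplemental oxygen use is also recorded at enrolment, so readings on oxygen can be flagged.

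The cost is SAP wording and one table. No new measurement is needed if the eligibility value is retained in the database; the data collection tables list vital signs but not the ARISCAT components, so this should be confirmed. The lowest band will have few patients per arm and phase and should be presented descriptively. The sensitivity estimate has a slightly smaller denominator, by the share f.

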#### 4.1.2. Secondary Objectives and Endpoints

The study secondary objectives are the followings:

1. To compare the two study Phases (see Section 5) in terms of primary endpoint incidence.
2. To compare the two study Phases in terms of respiratory AEs and SAE incidence, number of ICU transfers and related length of stay, Code blues and RRT responses.
3. To evaluate the impact of introducing continuous monitoring devices connected to a remote monitoring platform on the clinical workflow, defined as the rate of clinical early interventions performed by nursing staff to prevent a potential AE (e.g. patient stimulation, Jaw thrust maneuver, oxygen administration started or increased, medication change, etc.).

4. To evaluate the impact of introducing continuous monitoring devices connected to a remote monitoring platform on clinical staff workflow, defined as clinical staffs' satisfaction related to the monitoring system.
5. To characterize the predictive values of etCO2, RR, SpO2, plethysmography-derived RR, IPI and EWS in respect to respiratory AEs and other SAE.

Related secondary endpoints are:

1. Incidence of RC markers recorded by the monitoring system during each Phase.
2. Incidence of respiratory AEs and SAE, number of ICU transfers and related length of stay, Code blues and RRT responses recorded in the two study Phases.
3. Average rate of early interventions for patient will be calculated in both study Phases. In Phase I there should only be non-alarm-triggered interventions, as in clinical practice, while in Phase II there should be two sub-groups of clinical early interventions: alarm-triggered and non-alarm-triggered.
4. Clinical staff's satisfaction related to the monitoring system's introduction in their current workflow will be evaluated through a survey performed at the end of the study.
5. Sensitivity and specificity of each monitored parameter in predicting and identifying respiratory AEs and SAE will be calculated. EWS will be the only parameter not automatically collected by the monitoring system but manually collected.

